Over the first 30 days post discharge, participants in the intervention arm will receive 3 phone calls to promote PAP therapy and medication adherence. Participants in the standard of care (SOC) arm will also receive 3 phone calls to promote medication adherence over the first 30 days post discharge. On days 30 and 60, all participants will receive a phone call to determine if they had been admitted to the hospital, or had an unplanned visit to a physician’s office or emergency room. Information regarding hospital

A Pilot, Multi-Center, Randomized, Open-Label, Parallel Group Study to Assess the Effects of a Novel Application of Averaged Volume Assured Pressure Support Ventilation (AVAPS-AE) therapy on Re-hospitalization in Patients with Sleep-Disordered Breathing with co-morbid COPD.

Confidential

admission, diagnostic tests, medication changes, and procedures will be collected from all participants. Discharge summaries of re-hospitalizations and office or ER visits, as well as diagnostics tests and therapies received will be collected for measuring healthcare costs.

Participants who enrolled in a registry (optional) for a 3 year follow-up will also be queried on a yearly basis regarding hospitalizations, cardiovascular events, and assessment of vital statistics in the National Death Index registry. The study will conclude when all randomized participants have been followed for a minimum of 60 days. An independent Data Safety and Monitoring Committee (DSMC) will monitor safety data on an ongoing basis and may recommend that the study be stopped earlier in case of safety concerns. No Interim efficacy analyses is planned. Ongoing DSMB review is planned to assess device and/or safety related clinical events and adjudicate if applicable. This will be performed after 25%, 50% and 75% of target enrollment have been completed. Participants will be followed for occurrence of death or hospitalization throughout the duration of the study for a minimum of 24 months after randomization. All death and hospitalization reports will be collected on an ongoing basis during the study and will be adjudicated by an adjudication committee consisting of three site investigators.

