AVAPS-AE is a mode of therapy (Philips Resironics Inc, Monroeville, Pa) with potential advantages over the currently established modes of non-invasive positive pressure ventilation (CPAP and bilevel therapy). This mode of therapy incorporates AVAPS (automated adjustable IPAP setting to maintain target ventilation with a settable rate of change), Auto EPAP and Auto Back up Rate. We believe that these automated parameters will allow better nocturnal ventilatory control to offset the differing elastic and resistive loads imposed by changes in body position during sleep. Furthermore, AVAPS-AE will counter the changing ventilatory requirements due to alterations in lung volumes and airway resistance during different stages of sleep. In summary, the AVAPS-AE mode will enable automatic adjustment in response to ventilatory changes throughout the night. The device platform used in this study with the AVAPS-AE feature is in the BiPAP A40 platform. This device uses existing modes of therapy, therapy features, and algorithms as that which have been previously cleared by the Food and Drug Administration (FDA) (K121623).

III. Study Objectives/Endpoints

Specific aim #1: Evaluate the effects of novel application of Averaged Volume Assured Pressure Support (AVAPS-AE) therapy on time to (# of days) emergent and non-emergent healthcare utilization in patients with sleep-disordered breathing who are hospitalized with co-morbid COPD.

Specific aim #2: Evaluate the effects of novel application of Averaged Volume Assured Pressure Support (AVAPS-AE) therapy on the number of emergent and non-emergent healthcare utilization over 6 months;

A Pilot, Multi-Center, Randomized, Open-Label, Parallel Group Study to Assess the Effects of a Novel Application of Averaged Volume Assured Pressure Support Ventilation (AVAPS-AE) therapy on Re-hospitalization in Patients with Sleep-Disordered Breathing with co-morbid COPD.

Confidential

costs related to re-hospitalization; number of visits to physician offices or emergency rooms, and health-related quality of life (disease-specific and general HR-QOL measures).

Primary Endpoints

Composite end-point of time to occurrence of emergent healthcare utilization (such as re-hospitalization, unscheduled physician office visits, urgent care visits or emergency room visits).

Secondary Endpoints:

1. Healthcare Costs
2. Change in quality of life (SF-36) at 30 and 60-days
3. Change in quality of life (FOSQ) at 30 and 60-days

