4. Number of hospitalizations over 3 years (optional if enrolled in registry)
5. Time to re-hospitalization alone
6. Composite end-point of time to occurrence of non-emergent healthcare utilization (such as scheduled hospitalization, scheduled physician office, urgent care visits or emergency room visits).

IV. Subject Selection

Inclusion criteria:

1. Hospitalized patients who are at high risk for readmission who are at least 18 years of age.
2. Specifically patients with (a) a primary or secondary admission diagnosis of COPD who are ready for discharge AND (b) are also found to have sleep-disordered breathing (AHI \geq 10 per hour; $>3\%$ oxygen desaturation for hypopneas) by overnight portable respiratory study prior to hospital discharge.
3. Bedside spirometry revealing evidence for obstructive lung disease (post-bronchodilator; GOLD stage II or greater (FEV1 $<70\%$ predicted post BD).
4. No previous home PAP or NIV use within the past year

Exclusion criteria:

1. Central sleep apnea (Central apnea index >5 per hour; and/or $>50\%$ are central apneas & hypopneas)
2. Clinically unstable, i.e., hypotensive shock, uncontrolled cardiac ischemia or arrhythmias, requiring life support ventilation or as otherwise determined by the investigator
3. Participants with Stage III & IV Chronic Heart Failure as defined by the New York Heart Association (NYHA) Classification
4. Known or expected contraindications for the use of non-invasive ventilation per the assessment of the investigator.

A Pilot, Multi-Center, Randomized, Open-Label, Parallel Group Study to Assess the Effects of a Novel Application of Averaged Volume Assured Pressure Support Ventilation (AVAPS-AE) therapy on Re-hospitalization in Patients with Sleep-Disordered Breathing with co-morbid COPD.

Confidential

5. Lack of medical insurance

V. Study Enrollment

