- One week Device Adherence Assessment (Intervention Group)

During the first 2-7 business days post discharge, research staff will evaluate participant's device adherence via remote download. Participants with poor adherence to AVAPS-AE at home (adequate adherence defined as \geq 4 hours of use on at least 5 of the first 7 nights) will not be included in the "per-protocol analysis" (Such participants will, however, be considered in the intention to treat analysis). Per the investigators discretion, the device setting parameters may be adjusted at this time.

- Weekly Phone Follow-ups (Initial 30 days only):

Phone calls will be made weekly (\pm 2 business days) by the study coordinator to assess mask interface issues (Intervention group) and encourage adherence to AVAPS-AE (Intervention group) and medications (both intervention and SOC group). If participants require an additional visit related to issues noted above, this visit may occur either in the home or as an office to the study site.

- Day 30

At 30 days (\pm 2 business days) post discharge, participants in both Intervention and SOC groups will receive a phone call to determine if they had been admitted to this hospital, or had an unplanned visit to a physician's office or emergency room. Participants will be asked to complete FOSQ and SF-36 questionnaires. Participants will be given the option of completing the questionnaires verbally via phone call or completing handwritten copies and returned via direct mail. Postage paid return envelopes will be provided to participants who elect to complete and return the surveys by mail.

- Day 60

On day 60 (\pm 2 business days), participants in both Intervention and SOC groups will receive a phone call to determine if they had been admitted to this hospital, or had an unplanned visit to a physician's office or emergency room. Participants will be asked to complete a final FOSQ and SF-36 questionnaire. Participants will be given the option of completing the questionnaires verbally via phone call or completing handwritten copies and returned via direct mail. Postage paid return envelopes will be provided to participants who elect to complete and return the surveys by mail. Participants in both

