A Pilot, Multi-Center, Randomized, Open-Label, Parallel Group Study to Assess the Effects of a Novel Application of Averaged Volume Assured Pressure Support Ventilation (AVAPS-AE) therapy on Re-hospitalization in Patients with Sleep-Disordered Breathing with co-morbid COPD.

Confidential

intervention and SOC groups will receive \$150.00 as compensation for participating in the study. Compensation will be pro-rated based on completion of study milestones.

Information regarding admission, diagnostic tests, medication changes, and procedures will be collected from all participants. Discharge summaries of re-hospitalizations and office or ER visits and diagnostics tests and therapies received will be collected for measuring healthcare costs.

Participants will be asked if they would be interested enrolling in a registry for a 3 year follow-up. This will involve participants being contacted on a yearly basis inquiring about any hospitalizations, cardiovascular events, and assessment of vital statistics in the National Death Index registry. Participants who elect to enroll the registry will receive an additional \$25 in compensation.

Transition Plan:

Upon completion of the study or earlier termination, site investigators will cooperate with the study participants' primary health care providers regarding continuity of care to assure that participants receive appropriate follow-up care after the conclusion of the study. Study participants who are randomized to the treatment group, where a therapeutic benefit is evident, will be allowed to keep the provided AVAPS device until a similar replacement device can be provided to the participant through usual care pathways as part of this transition plan. Study participants who are randomized to the SOC group will have the option of receiving an AVAPS unit at the end of the 60 day period if prescribed and provided through the usual care pathway of their healthcare provider as part of this transition plan. The risk of additional and on-going device supplies not being covered by insurance or involving co-pays will be explained to the participant within the consent. Philips will not be responsible for providing device maintenance or study supplies after the 60 day study period.

Study Process Flow:

Study Procedures	Hospital Procedures (Pre-Discharge)	Post Discharge Study Procedures	Post 60 Day Study Procedures
Informed consent	X		
Inclusion/Exclusion Review	X		
Medical History Assessment	X		
Vitals	X		

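### The Day-30 and Day-60 calls ask about admissions and unplanned visits only, so scheduled office visits, which secondary endpoint 6 and the non-emergent parts of Aims 1 and 2 need, are not systematically ascertained

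*Combined protocol and SAP*

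**What the plan says.** **What has to be measured (III. Study Objectives/Endpoints).** Aim 1 concerns the effect of "therapy on time to (# of days) emergent and non-emergent healthcare utilization in patients with sleep-disordered breathing". Aim 2 concerns the effect of "therapy on the number of emergent and non-emergent healthcare utilization over 6 months" and goes on to list "number of visits to physician offices or emergency rooms, and health-related quality of life", without limiting the visits to unplanned ones. Secondary endpoint 6 is "time to occurrence of non-emergent healthcare utilization (such as scheduled hospitalization, scheduled physician office, urgent care visits or emergency room visits". The primary composite is time to emergent use and lists re-hospitalization without saying whether planned admissions count.

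**What is asked.** In VI. Study Procedures, under Day 30 and again under Day 60, participants in both arms "will receive a phone call to determine if they had been admitted to this hospital, or had an unplanned visit to a" doctor's office or the ER. II. Study Design describes the same contacts in nearly the same terms: "all participants will receive a phone call to determine if they had been admitted to the hospital, or had an unplanned visit".

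**What else is collected.** Under Day 60, VI. Study Procedures adds: "Discharge summaries of re-hospitalizations and office or ER visits and diagnostics tests and therapies received will be collected for measuring healthcare costs". II. Study Design has a matching sentence. It also provides for a committee of three site investigators to adjudicate all deaths and hospitalizations.

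**The concern.** A time-to-event endpoint needs a process that finds the events and dates them. Endpoint 6 names scheduled office visits, yet the only contacts that ask about office visits ask about unplanned ones. If sites follow the text as written, a participant who attends a planned clinic appointment is not asked about it, and the visit enters the data only if a record happens to reach the study by another route. Endpoint 6 would then partly measure how complete each site's record retrieval was.

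Admissions raise a related problem. The call asks about any admission, but the same admission belongs to the primary composite if it is emergent and to endpoint 6 if it was scheduled. The plan describes no field that records which it was.

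At stake are the interpretability of endpoint 6, the non-emergent half of Aim 1 and the office-visit count in Aim 2. Visits that were not asked about during follow-up are hard to recover afterwards.

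**Working it through.** The plan gives no expected rate for scheduled or non-emergent care, so there is no figure to reproduce. The 20.5% 30-day readmission rate that it cites concerns readmissions and says nothing about scheduled office visits. The check is a comparison of text, plus one calculation on the observation window.

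**Step 1. Each described source against what endpoint 6 needs.**

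| Source | Section | Covers | Scheduled office visits? |
|---|---|---|---|
| Day-30 and Day-60 calls | II; VI | Admissions; unplanned office or ER visits | Not asked |
| Weekly calls, first 30 days | VI | Mask problems, adherence | Not asked |
| Visit and discharge records | II; VI | Re-hospitalizations, office and ER visits, tests, therapies, for costing | Possible, but no step to find them |
| Study Process Flow rows for the calls | VI | General label: healthcare utilization assessment | Content not specified |
| Follow-up after day 60 | II | Death, hospitalization | Not covered |
| Optional registry | II; VI | Hospitalizations, cardiovascular events, vital status | Not covered |

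The records row is the only route to a scheduled office visit. A record can be requested only once someone knows the visit took place, and the contact that would reveal it is worded to exclude it.

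**Step 2. Admissions.** The admission question is not limited to unplanned admissions, so scheduled admissions fall within it. What is missing is the classification: neither the call descriptions nor the adjudication sentence mentions planned versus unplanned status.

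**Step 3. Two smaller mismatches in the same call text.** Urgent-care visits appear in both the primary composite and endpoint 6, but neither call description names them. Section VI refers to admission to this hospital and Section II to the hospital, so the intended scope of the admission question is unclear.

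**Step 4. Aim 2's window.** Inputs: calls end at day 60 (VI), analysis is at 30 and 60 days (VII. Statistical Analysis), and Aim 2 counts events over 6 months (III). Taking 6 months as 180 to 184 days:

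- Share covered by the calls: 60/180 = 33.3%; 60/184 = 32.6%.
- Share not covered: 1 − 60/180 = 66.7%; 1 − 60/184 = 67.4%.

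For about two thirds of the Aim 2 window, no collection of office visits of either kind is planned. Hospitalizations are still followed.

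**The case against.** The best defence is that the calls are not the only source. The costing records are not restricted to unplanned visits, the schedule describes the calls in general terms, the admission question takes in scheduled admissions, and hospitalizations are adjudicated with discharge summaries to hand. The call script and CRF are not part of the documents, and a short description of a call's purpose need not be the whole script. The unplanned wording also suits the primary endpoint, which concerns emergent use.

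Much of this stands, and it rules out several stronger readings:

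- A reader might infer that scheduled care is never asked about, or that endpoint 6 cannot be measured. The documents do not support that. Scheduled admissions come within the admission question, and some scheduled office visits may surface in records.
- A reader might infer that Aim 2's office-visit count cannot be obtained. Unplanned office visits are asked about to day 60, so the count is incomplete rather than absent. Nor is it shown that the cost total loses scheduled care, because the records are collected for costing.
- A reader might put a number on the participants affected. That needs the share with a scheduled visit and the fraction recovered from records, and the documents give neither.
- A reader might infer bias between arms, since standard-of-care participants may be seen at a sleep center and intervention participants may have extra visits for mask or adherence problems. That is plausible, but nothing supports a direction or size.
- A reader might say that missed cases are censored as event-free. No censoring rule for endpoint 6 is stated.

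The defence does not supply a step that identifies scheduled office visits or a stated criterion that separates planned from unplanned admissions. The general schedule label refers to the same calls whose content is spelled out twice in narrower terms.

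**Conclusion.** The point holds in a limited form. As written, the plan does not systematically ascertain scheduled office visits, a named component of endpoint 6 and part of the non-emergent use in Aims 1 and 2. Endpoint 6 and the non-emergent part of Aim 1 are likely to be under-counted, and Aim 2's office-visit count is incomplete. The size of the under-count up to day 60 cannot be derived from the documents. Beyond day 60, about 67% of Aim 2's stated window has no planned collection of office visits.

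This assumes that sites ask what the protocol describes and that no unpublished script or CRF asks more. If a fuller script exists, the remedy is to bring the protocol into line with it.

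The matter should be fixed, but it does not undermine the trial's main comparison. Endpoint 6 is the last of six secondary endpoints in a pilot, and the calls do ask about unplanned office and ER visits, which the primary composite needs. The primary endpoint is touched only where planned admissions cannot be told from unplanned ones.

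**What to change.** 1. Reword the Day-30 and Day-60 calls, in both Sections II and VI, and the CRF, to record every hospital admission and every office, urgent-care and ER visit since the last contact. Give each entry its date and a planned/unplanned flag, and state whether admissions to any hospital count.
2. Derive endpoint 6 and the utilization counts from that log, and use the flag to assign admissions to the primary composite or to endpoint 6. Use the log to request visit records.
3. Restate Aim 2's count over the 60 days that the calls and analysis cover, or add a contact at 6 months. Rewording the existing calls cannot by itself deliver a 6-month count.
4. If the sponsor does not want to collect this, delete endpoint 6 and remove non-emergent use from Aims 1 and 2.

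The cost is a short repeating event log on calls already scheduled, somewhat longer calls, and a protocol amendment. The 6-month option adds one contact per participant.

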Participants who are screened for enrollment will be entered on a screening log which will be maintained at the clinical site. Participants referred for screening will be given a thorough explanation of the study and the requirements for participation by the study coordinator or other qualified medical professional. If the participant is interested in the study, the investigator or a member of his/her staff should approach the patient to obtain written informed consent. The background of the proposed study, the benefits and risks of the procedures and study should be thoroughly explained to the participant. The participant must sign the consent form prior to enrollment. This form or a modification of it must have prior approval of the study site's Institutional Review Board (IRB). Failure to provide informed consent renders the participant ineligible for the study.

Up to 10 sites will be recruiting for this study. Up to 80 participants will be enrolled across all sites with the goal of 60 participants (N=60) completing the study (25% attrition rate). One site should not enroll more than 25% of total N.

VI. Study Procedures

Screening Assessment

Hospitalized patients with comorbid COPD who are at high risk for readmission will be recruited. Specifically patients with comorbid COPD who are about to be discharged, with (a) prior hospitalization (within the past 12 months) Such participants will undergo questionnaire-based screening for sleep-disordered breathing (STOP-BANG questionnaire) and if they have a high risk for SDB (≥ 3 points) will undergo an overnight screening portable sleep study the night prior to hospital discharge (AHI ≥ 10 per hour; $>3\%$ oxygen desaturation for hypopneas). Sites may exercise the option of using the STOP-BANG questionnaire as a screening tool for the purposes of enriching the study population.

Spirometry

Each participant will undergo a spirometric assessment, using a handheld Koko™ unit, to determine if they meet inclusion criteria.

Spirometry will be performed based on the "Standardization of Spirometry – 2005".¹¹ Acceptability and reproducibility criteria are summarized in Table 8 of the ATS document. Spirometry equipment must be calibrated with a 3L syringe prior to the first use daily. The results will be printed and maintained in a calibration log, which will routinely be monitored for compliance during monitoring visits. Spirometry

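### Urgent care is named in the primary composite but not in the Day-30/Day-60 calls, the records or the analysis text, and the call text words admissions inconsistently

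*Combined protocol and SAP*

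**What the plan says.** **Endpoint.** Section III (Primary Endpoints) defines a composite time to emergent utilization, "such as re-hospitalization, unscheduled physician office visits, urgent care visits or emergency room visits". Re-hospitalization carries no limit to a particular hospital. Urgent care is named here and in secondary endpoint 6, and nowhere else.

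**Calls.** Section VI (Post Discharge Study period) describes the Day-30 and Day-60 calls in the same words: they are made "to determine if they had been admitted to this hospital, or had an unplanned visit to a" physician's office or emergency room. Section II describes the same calls differently: "all participants will receive a phone call to determine if they had been admitted to the hospital". That sentence also continues with unplanned office and ER visits only.

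**Records.** Section II collects "Discharge summaries of re-hospitalizations and office or ER visits, as well as diagnostics tests and therapies received", for measuring costs. Section VI repeats this in nearly the same words. Both sections also collect information on admissions from all participants.

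**Other capture.** Section II says participants are followed for death or hospitalization, and that "All death and hospitalization reports will be collected on an ongoing basis during the study". It does not say where the reports come from.

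**Analysis.** Section VII (Statistical Analysis) handles repeated hospitalizations, office visits and ER visits, and counts every repeat hospitalization without a hospital limit.

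**Schedule.** The Study Process Flow table calls both contacts a healthcare utilization assessment and lists no components.

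**The concern.** A component of a primary composite needs a path from definition to question, to source record, to analysis. Urgent care has the first step and is not named in the other three. A coordinator who follows Section VI literally would not ask about it. A participant who volunteers a visit would be classified by whatever the coordinator or participant takes an office or ER visit to be.

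The wording on admissions is a lesser problem of the same kind. Section V says "Up to 10 sites will be recruiting for this study", so *this hospital* naturally reads as the enrolling hospital. That is narrower than the endpoint.

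Because the endpoint is a time to first event, a missed visit can do harm in two ways. The participant may be counted as event-free, or a later captured event may be taken as the first and dated too late. The call text asks whether an event occurred and does not mention its date.

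**Working it through.** **Step 1: set the texts side by side.**

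| Place | Admission | Office | ER | Urgent care |
|---|---|---|---|---|
| III, primary endpoint | any hospital | unscheduled | yes | named |
| II, Day-30/60 calls | *the* hospital | unplanned | unplanned | not named |
| VI, Day-30/60 calls | *this* hospital | unplanned | unplanned | not named |
| II and VI, records | re-hospitalizations | yes | yes | not named |
| II, follow-up and ongoing reports | hospitalization, no limit | – | – | not named |
| VII, analysis | all repeat hospitalizations | yes | yes | not named |
| Study Process Flow | generic label | generic label | generic label | generic label |

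The urgent care column has no entry below the endpoint row except the generic label. In the admission column, only the Section VI call text is narrower than the endpoint.

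**Step 2: the plan's own figures.** Section V plans up to 80 enrolled for 60 completers at 25% attrition: 60/(1 − 0.25) = 80, which reproduces. The plan states no alpha, power, effect size or event target, so there is no power figure to reproduce. Section VII (Risks and Discomforts) expects a 30-day readmission rate of 20.5%. For 60 completers that is 60 × 0.205 = 12.3 readmitted participants.

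**Step 3: illustrate the loss.** The documents give no frequency of outside admissions or urgent care visits. The inputs below are assumptions, apart from the 20.5% and the 60 completers.

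- 30 completers per arm.
- Standard-of-care 60-day risk p = 1 − (1 − 0.205)² = 0.368 under a constant hazard. This is readmission only, so low for the composite. A second value of 0.55 is assumed.
- Net share u of the event hazard missed after any backup: 0, 5%, 10% or 20%, equal in both arms.
- Hazard ratio (HR) 0.50, the same for missed and captured event types; two-sided 5% test.

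Formulas: h_S = −ln(1 − p)(1 − u); h_A = HR × h_S; events per arm d = 30(1 − e^(−h)); SE = √(1/d_S + 1/d_A); 95% CI = HR × exp(±1.96 SE); power = Φ(|ln HR|/SE − 1.96).

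Example, p = 0.368 and u = 0: h_S = 0.459, d_S = 11.04, d_A = 6.15, total 17.19. SE = 0.503, CI 0.19 to 1.34, power Φ(0.693/0.503 − 1.96) = 0.28.

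| p | u | First events | Lost | 95% CI at HR 0.50 | Power |
|---|---|---|---|---|---|
| 0.368 | 0 | 17.2 | – | 0.19–1.34 | 28.0% |
| 0.368 | 5% | 16.5 | 0.7 | 0.18–1.37 | 27.0% |
| 0.368 | 10% | 15.7 | 1.4 | 0.18–1.40 | 26.0% |
| 0.368 | 20% | 14.2 | 2.9 | 0.17–1.48 | 23.9% |
| 0.55 | 0 | 26.4 | – | 0.23–1.10 | 40.6% |
| 0.55 | 5% | 25.4 | 1.0 | 0.22–1.12 | 39.3% |
| 0.55 | 10% | 24.4 | 2.0 | 0.22–1.14 | 38.0% |
| 0.55 | 20% | 22.4 | 4.0 | 0.21–1.18 | 35.2% |

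At HR 0.70 the event loss is similar: 19.3 falls to between 18.5 and 16.0 (p = 0.368), and 29.3 to between 28.3 and 25.0 (p = 0.55).

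**Step 4: when the hazard ratio moves.** Let w be the captured share of the standard-of-care hazard. The composite HR is then w × HR_captured + (1 − w) × HR_missed, while the trial would observe HR_captured. The two agree only if HR_missed = HR_captured, and then only if capture is the same in both arms. Step 3 assumes both. If either fails, the estimate shifts, in a direction that the documents do not determine.

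**The case against.** The best case for the plan has four parts.

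*Admissions are not really restricted.* Section II says *the* hospital, follows participants for hospitalization and collects reports on an ongoing basis. Admission information and discharge summaries are collected. Section VII counts all repeat hospitalizations. One word in Section VI stands alone and may be a slip. This largely stands. A reader might infer that admissions to other hospitals will be lost, but the documents do not support that. They show a wording conflict with partial backup, the source of the ongoing reports being unstated.

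*The calls are a healthcare utilization assessment.* That is the endpoint's own term, so urgent care could be included. This is possible, and it is why urgent care should be called not named, and not excluded. But the label lists no components, and both detailed descriptions of the calls leave urgent care out.

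*The text is a summary.* The call script and case report form are not in the documents, the endpoint list is introduced as examples, and a participant may report urgent care as an office or ER visit. All true, so actual loss cannot be shown. An open list makes a fixed set of questions more necessary, since sites may otherwise classify visits differently.

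*The effect is small in a pilot.* In the illustration the intervals include 1 with or without the loss, and no planned decision rests on a power target. This stands and limits the point to a modest loss. With so few events expected, it does not make an almost free correction unnecessary.

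**Conclusion.** The mismatch is certain on the text; its consequence is not. Urgent care is the firmer gap, because neither the call descriptions nor the records or analysis text names it. The admission wording is an internal conflict to reconcile.

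The true loss is unknown. Under the stated assumptions it is about 1 to 4 first events and about 1 to 5 percentage points of power.

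Two stronger readings should be avoided. A reader might infer bias between the arms from the open-label design, but the calls are described identically for both arms and nothing in the documents shows that capture differs. A reader might equally infer that equal loss is harmless to the hazard ratio. That holds only if the treatment effect is also the same for missed and captured event types; otherwise the composite estimate can shift in an unknown direction.

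This should be fixed. It is not a fatal defect.

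**What to change.** Use one component list in the endpoint definition, the call description in Sections II and VI, the records to be collected, and the Statistical Analysis section. There are two acceptable routes for urgent care, to be chosen before data review:

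1. Keep it as a component. Both calls then ask both arms, with dates, about admission to any hospital and about ER, unscheduled office and urgent care visits. Urgent care is added to the records and the analysis text.
2. Remove it from the endpoint, or define it as an office or ER visit.

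Under either route, replace the *this hospital* wording so that the calls ask about any hospital, ask for dates, and state the source of the ongoing hospitalization reports.

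The cost is a wording change. The calls are already made to every participant, so the downside is slightly longer calls and a few more records to request.
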